#### 4.1.3 Method of assigning subjects to treatment sequences

Prior to the screening visit, subjects will be contacted in writing and informed about the planned visit dates. Subjects willing to participate will be recruited to the trial.

The randomisation list will be provided to the trial site in advance.

Subjects will be allocated to treatment sequences prior to the first administration of trial medication in the morning of Day 1 (Visit 2). For this purpose, numbers of the randomisation list will be allocated to the subjects by the method 'first come - first served' at the time of registration. Therefore, the allocation of subjects to treatment sequences is not influenced by trial personnel, but only by subjects' temporal availability. Subjects are then assigned to a treatment sequence according to the randomisation list.

Once a subject number has been assigned, it cannot be reassigned to any other subject.

The randomisation procedure is described in Section 7.6.

#### 4.1.4 Drug assignment and administration of doses for each subject

This trial is a two-way cross-over study. All subjects will receive the 2 treatments in randomised order. The treatments to be evaluated are outlined in Table 4.1.4: 1 below.

Table 4.1.4: 1 Dosage and treatment schedule

Treatment	Substance	Formulation	Unit strength	Dosage	Total dose
R (Reference)	BI 1595043	film-coated tablet	5 and 25 mg	1 tablet 5 mg and 1 tablet 25 mg under fasted condition (single dose)	30 mg
T (Test)	BI 1595043	film-coated tablet	5 and 25 mg	1 tablet 5 mg and 1 tablet 25 mg under fed condition (single dose)	30 mg

In treatment R (in the fasted state), administration of trial medication will be performed after subjects have fasted overnight; fasting is to start no later than 10 h before the scheduled dosing.

In treatment T (in the fed state), a high-fat, high-calorie meal will be served 30 min before drug administration. The subjects must completely consume the meal prior to drug intake. The composition of the standard high-fat, high-calorie meal is detailed in Table 4.1.4: 2; this meal is in compliance with the FDA guidance 'Food-Effect Bioavailability and Fed Bioequivalence Studies' [R03-2269]. For restrictions with regard to diet, see Section 4.2.2.2.

Table 4.1.4: 2 Composition of the high-fat, high-calorie meal

Ingredients	kcal
2 chicken eggs (whole content) for scrambled eggs	192
10 g butter for frying scrambled eggs	75
35 g fried bacon	186
2 toasted slices of wheat bread	130
15 g butter for buttering toast slices	113

388550-04 Trial Protocol Page 40 of 75

Proprietary confidential information © 2021 Boehringer Ingelheim International GmbH or one or more of its affiliated companies

Ingredients	kcal
115 g hash brown potatoes	132
240 mL whole milk (3.5% fat)	156
Sum ¹	984

The total caloric content was supplied approximately as following: 150 kcal as protein, 250 kcal as carbohydrate, and 500 to 600 kcal as fat.

*In each treatment period,* the investigator (or authorised designee) will administer the trial medication as an oral dose together with about 240 mL of water to subjects who are in a sitting or standing position.

For drug administration, the so-called four-eye principle (two-person rule) should be applied. For this, one authorised employee of the trial site should witness the administration of trial medication, and – if applicable – its preparation (dispensing of BI 1595043), if correct dosage cannot be ensured otherwise.

Subjects will be kept under close medical surveillance until 48 h after drug administration. During the first 2 h after drug administration, subjects are not allowed to lie down (i.e. no declination of the upper body of more than 45 degrees from upright posture except for medical examination) or to sleep.

The treatments will be separated by a wash-out phase of at least 8 days.

#### 4.1.5 Blinding and procedures for unblinding

This Phase I trial will be handled in an open fashion throughout (that is, during the conduct, including data cleaning and preparation of the analysis). This is considered acceptable because the potential for bias seems to be low and does not outweigh practical considerations.

All trial data will be handled open label. This means that trial functions of the sponsor are unblinded (e.g. clinical trial lead, data manager, statistician, bioanalyst, pharmacokineticist, pharmacometrician, drug metabolism scientist as well as dedicated personnel of the trial site).

Emergency envelopes will not be provided, because the dose of trial medication is known to investigators and subjects.

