# 3.2 DISCUSSION OF TRIAL DESIGN, INCLUDING THE CHOICE OF CONTROL GROUP(S)

For relative bioavailability trials, the crossover design is preferred because of its efficiency: since each subject serves as his own control, the comparison between treatments is based on an intra-subject comparison, thus removing inter-subject variability from the comparison between treatments [R94-1529].

Blinding is not possible because the treatments are distinguishable. The open-label treatment is not expected to bias the results, since the PK endpoints are derived from measurement of plasma concentrations of the analyte which are provided by a bioanalytical laboratory that is blinded to treatment allocation.

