#### 5.3.2 Methods of sample collection

#### 5.3.2.1 Blood sampling for pharmacokinetic analysis

For quantification of BI 1595043 concentrations in plasma, 2.7 mL of blood will be drawn from an antecubital or forearm vein into an K₂-EDTA (dipotassium ethylenediaminetetraacetic acid)-anticoagulant blood drawing tube at the times indicated in the Flow Chart. Blood will be withdrawn by means of either an indwelling venous catheter or by venepuncture with a metal needle.

The EDTA-anticoagulated blood samples will be centrifuged for approximately 10 min at approximately 2000 g to 4000 g and at 4 to 8 °C. Two plasma aliquots will be obtained and stored in polypropylene tubes. The first aliquot should contain at least 0.5 mL of plasma, the second aliquot will contain the remaining plasma. The process from blood collection until transfer of plasma aliquots into the freezer should be completed in less than 90 min, with interim storage of blood samples and aliquots at room temperature. The time each aliquot was placed in the freezer will be documented. Until transfer on dry ice to the analytical laboratory, the aliquots will be stored upright at approximately -20°C or below at the trial site. The second aliquot will be transferred to the analytical laboratory after the bioanalyst has acknowledged safe arrival of the first aliquot. At the analytical laboratory, the plasma samples will be stored at approximately -20°C or below until analysis.

At a minimum, the sample tube labels should list BI trial number, subject number, day, and planned sampling time. Further information such as matrix and analyte may also be provided.

Plasma samples will be transferred to

After completion of the trial, the plasma samples may be used for further methodological investigations (e.g., assessment of metabolites). However, only data related to the analyte and/or its metabolite(s) will be generated by these additional investigations. The study samples will be discarded after completion of the additional investigations, but not later than 5 years after the CTR is archived.

Boehringer Ingelheim BI Trial No.: 1445-0011 30 June 2021

Page 53 of 75

Proprietary confidential information © 2021 Boehringer Ingelheim International GmbH or one or more of its affiliated companies

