#### 8.1 TRIAL APPROVAL, SUBJECT INFORMATION, INFORMED CONSENT

This trial will be initiated only after all required legal documentation has been reviewed and approved by the responsible Institutional Review Board (IRB) / Independent Ethics Committee (IEC) and competent authority (CA) according to national and international regulations. The same applies for the implementation of changes introduced by amendments.

Prior to a subject's participation in the trial, written informed consent must be obtained from each subject (or the subject's legally accepted representative) according to ICH-GCP and to the regulatory and legal requirements of the participating country. Each signature must be personally dated by each signatory and the informed consent and any additional subject-information form retained by the investigator as part of the trial records. A signed copy of the informed consent and any additional subject information must be given to each subject or the subject's legally accepted representative.

The subject must be given sufficient time to consider participation in the trial. The investigator or delegate obtains written consent of the subject's own free will with the informed consent form after confirming that the subject understands the contents. The investigator or delegate must sign (or place a seal on) and date the informed consent form. If a trial collaborator has given a supplementary explanation, the trial collaborator also signs (or places a seal on) and dates the informed consent.

Re-consenting may become necessary when new relevant information becomes available and should be conducted according to the sponsor's instructions.

Page 63 of 75

Proprietary confidential information © 2021 Boehringer Ingelheim International GmbH or one or more of its affiliated companies

The consent and re-consenting process should be properly documented in the source documentation.

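### Does naming the bioanalyst as unblinded in Protocol 4.1.5 undo the blinded laboratory that Section 3.2 relies on?

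*Protocol*

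**What the plan says.** Protocol Section 3.2 first explains that treatment cannot be blinded because fed and fasted dosing can be told apart. It then addresses bias: "The open-label treatment is not expected to bias the results, since the PK endpoints are derived from measurement of plasma concentrations", and these are "provided by a bioanalytical laboratory that is blinded to treatment allocation".

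Protocol Section 4.1.5 describes how the data are handled. "All trial data will be handled open label", and it follows that "trial functions of the sponsor are unblinded (e.g. clinical trial lead, data manager, statistician, bioanalyst, pharmacokineticist" and further roles, including dedicated personnel at the trial site. Its reason is brief: "This is considered acceptable because the potential for bias seems to be low and does not outweigh practical considerations". It does not mention the laboratory.

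The bioanalyst appears once more, in Section 5.3.2.1: "The second aliquot will be transferred to the analytical laboratory after the bioanalyst has acknowledged safe arrival of the first aliquot". The same section sets the minimum label content: "the sample tube labels should list BI trial number, subject number, day, and planned sampling time".

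SAP Section 8 loads treatment information into the trial database once enrolment and randomisation are complete. The SAP says nothing further on who is blinded.

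**The concern.** AUC0-tz, Cmax and AUC0-∞ are all calculated from the measured concentrations. In an open-label trial, the assay is the step where a blind can still be kept, and the blinded laboratory is the only reason Section 3.2 gives for expecting no bias. Section 4.1.5 is the section headed as dealing with blinding. It puts a bioanalyst on the unblinded side, makes no exception for assay work, and gives a different reason for accepting open handling. Section 5.3.2.1 places a bioanalyst in the sample chain.

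If that person also took part in re-assay, re-integration or rejection of samples, treatment knowledge could enter those decisions and the argument in Section 3.2 would lose its footing. Neither document says that the bioanalyst is separate from the people who run the assay.

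**Working it through.** This is mainly a comparison of texts. No figure in the plan depends on it.

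**Step 1: who each section covers.**

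| Place | Subject of the statement | Status or task |
|---|---|---|
| 3.2 | Bioanalytical laboratory | Blinded to allocation |
| 4.1.5 | Sponsor functions (bioanalyst among them) and site personnel | Unblinded |
| 5.3.2.1 | Bioanalyst | Acknowledges arrival of the first aliquot |
| 5.3.2.1 | Analytical laboratory | Receives, stores and analyses the samples |

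The laboratory and the bioanalyst are named separately throughout. Section 4.1.5 does not name the laboratory, and Section 3.2 does not name the bioanalyst. A sponsor bioanalyst who knows the allocation and liaises with a laboratory that does not know it satisfies every row.

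**Step 2: which statement is the more specific.** Section 3.2 makes a direct statement about the laboratory. Section 4.1.5 is general, and when it spells out open handling it refers to conduct, data cleaning and preparation of the analysis, not to the assay. Read together, the specific statement stands within the general one. Their conclusions also agree: both regard the risk of bias as low.

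**Step 3: whether the described procedures break the laboratory blind.** Acknowledging a shipment does not alter a concentration. The minimum label gives trial, subject, day and planned time, with no treatment or sequence. Subject and day identify the treatment only to someone who also holds the allocation, and Section 3.2 says the laboratory does not.

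**Step 4: how many measurements are covered.** The Flow Chart has 14 samples from pre-dose to 12 h (pre-dose; 0:15, 0:30, 0:45, 1:00, 1:15, 1:30, 2:00, 2:30, 3:00, 4:00, 6:00, 8:00, 12:00) and 8 later ones (24, 34, 48, 72, 96, 120, 144, 168 h), so 22 per period. Over the trial, 22 × 2 periods × 14 subjects = 616. This is a count of samples, not a size of bias.

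**Step 5: what a single altered value could do.** First, the plan's own precision at N = 14 and gCV 23% (Protocol Table 7.7: 1):

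- Within-subject SD on the log scale: √ln(1 + 0.23²) = 0.2270.
- Standard error of the treatment difference: 0.2270 × √(2/14) = 0.0858.
- Half-width with t(0.95; 12 df) = 1.782: 0.1529.
- Allowance for 95% probability with χ²(0.95; 12 df) = 21.03: 0.1529 × √(21.03/12) = 0.2025.
- exp(0.2025) = 1.224, which matches the table.

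In a balanced 2×2 crossover (7 per sequence, complete data), each log value enters the treatment difference with weight 1/14. Changing one subject's value in one treatment by a factor 1 + x shifts the ratio by exp(ln(1 + x)/14) − 1:

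| Assumed change x | Shift in T/R |
|---|---|
| 10% | 0.7% |
| 20% | 1.3% |
| 30% | 1.9% |

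The values of x are assumptions; neither document gives them. If k subjects were changed in the same direction, the exponent would be k/14, so a 10% change in all 14 would shift the ratio by the full 10%. Nothing in the documents points to such a pattern.

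**The case for a change.** The strongest case for acting is that the separation of roles has to be inferred. Someone working from Section 4.1.5 alone would not learn that a laboratory blind must be kept. The label does not prevent identification by anyone holding the randomisation list, and SAP Section 8 ties release of treatment information to the end of enrolment, not to the end of the assay. A sponsor that cites a blinded assay as its safeguard might be expected to state it in the blinding section. One sentence would do so.

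It stands that the two sections are not cross-referenced and that the bioanalyst's role is left undefined. It does not stand that the plan contradicts itself or leaves the assay open. The feared route, an unblinded person deciding on re-assay or rejection, is described in neither document. The laboratory's name has been removed from Sections 5.3.2.1 and 8.7, so readers of the full protocol may see the separation more plainly than we can. The two possible edits also point in opposite directions: write down a separation that Section 3.2 already implies, or delete the argument from Section 3.2. Neither alters the design, the sample size or the analysis. A protocol change would still go through the approvals in Section 8.1: "The same applies for the implementation of changes introduced by amendments".

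**Conclusion.** No change follows. The mismatch is one of wording, and following both sections keeps the laboratory blinded to allocation. This rests on reading the bioanalyst in Section 4.1.5 as a sponsor role distinct from the laboratory staff. The documents' separate terms support that reading but do not state it. If the reading were wrong, Section 3.2 would lose its stated reason for expecting no bias. The endpoints would still be derived from measured plasma concentrations, and Section 4.1.5 gives its own rationale.

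The size of any bias cannot be derived from the documents. On the single-subject illustration it is at most 1.9% in the ratio, small beside an upper limit 22.4% above the estimate. Protocol Section 7.2 specifies no formal test or acceptance range, so a shift of that order would not turn a decision.

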#### 4.1.6 Packaging, labelling, and re-supply

The investigational medicinal products will be provided by BI. They will be packaged and labelled in accordance with local law and the principles of Good Manufacturing Practice.

For details of packing and the description of the label, refer to the ISF.

The telephone number of the sponsor and the name, address and telephone number of the trial site are provided in the subject information form. The EudraCT number is indicated on the title page of this protocol as well as on the subject information and informed consent forms.

No re-supply is planned.

8550-04 Trial Protocol Page 41 of 75

Proprietary confidential information © 2021 Boehringer Ingelheim International GmbH or one or more of its affiliated companies

#### 4.1.7 Storage conditions

Drug supplies will be kept in their original packaging and in a secure limited access storage area in accordance with the recommended (labelled) storage conditions. If necessary, a temperature log must be maintained to make certain that the drug supplies are stored at the correct temperature. If the storage conditions are found to be outside the specified range, the local clinical monitor (as provided in the list of contacts) is to be contacted immediately.

#### 4.1.8 Drug accountability

The investigator or designee will receive the investigational drugs delivered from the sponsor following requirements are fulfilled:

- Approval of the clinical trial protocol by the IRB / ethics committee
- Availability of a signed and dated clinical trial contract between the sponsor and the investigational site
- Approval/notification of the regulatory authority, e.g. competent authority
- Availability of the curriculum vitae of the Principal Investigator
- Availability of a signed and dated clinical trial protocol

Only authorised personnel documented in the form 'Trial Staff List' may dispense medication to trial subjects. The trial medication must be administered in the manner specified in the CTP.

The investigator or designee must maintain records of the product's delivery to the trial site, the inventory at the site, the use by each subject, and the disposal of unused products. These records will include dates, quantities, batch / serial numbers, expiry ('use-by') dates, and the unique code numbers assigned to the investigational medicinal product and trial subjects. The investigator or designee will maintain records that document adequately that the subjects were provided the doses specified by the CTP and reconcile all investigational medicinal products received from the sponsor. At the time of disposal of remaining trial medication, the investigator or designee must verify that no remaining supplies are in the investigator's possession.

All unused medication will be disposed of locally by the trial site upon written authorisation of the trial clinical monitor. Receipt, usage and disposal of trial medication must be documented on the appropriate forms. Account must be given for any discrepancies.

# 4.2 OTHER TREATMENTS, EMERGENCY PROCEDURES, RESTRICTIONS

#### 4.2.1 Other treatments and emergency procedures

There are no special emergency procedures to be followed. No additional treatment is planned. However, if adverse events require treatment, the investigator can authorise symptomatic therapy. In those cases, subjects will be treated as necessary and, if required,

Page 42 of 75

Proprietary confidential information © 2021 Boehringer Ingelheim International GmbH or one or more of its affiliated companies

kept under supervision at the trial site or transferred to a hospital until all results of medical evaluations are acceptable.

#### 4.2.2 Restrictions

#### 4.2.2.1 Restrictions regarding concomitant treatment

In principle, no concomitant therapy is allowed. All concomitant or rescue therapies will be recorded (including time of intake on study days) on the appropriate pages of the CRF.

Acetaminophen (paracetamol) is prohibited as concomitant mediation in this study. If necessary, short-term use of ibuprofen or acetylsalicylic acid is acceptable.

Drugs with a known hepatotoxicity profile should be avoided during the entire study.

#### 4.2.2.2 Restrictions on diet and life style

While admitted to the trial site, the subjects will be instructed not to consume any foods or drinks other than those provided by the staff. Standardised meals will be served at the times indicated in the Flow Chart. No food is allowed for at least 4 h after drug intake.

From 1 h before drug intake until lunch, fluid intake is restricted to the milk served with breakfast (see Table 4.1.4: 2), the water administered with the drug, and an additional 240 mL of water at 2 h and 4 h post-dose (mandatory for all subjects).

Alcoholic beverages, grapefruits, Seville oranges (sour or bitter oranges) and their juices, and dietary supplements and products containing St. John's wort (*Hypericum perforatum*) are not permitted from 7 days before the first administration of trial medication until after the last PK sample of each study period is collected.

Methylxanthine-containing drinks or foods (such as coffee, tea, cola, energy drinks, or chocolate) are not allowed from 10 h before until the end of the in-house period at the trial site. Smoking is not allowed during in-house confinement while admitted to the trial site.

Excessive physical activity (such as competitive sport) should be avoided from 7 days before the first administration of trial medication until the end of trial examination.

Subjects with pregnant or non-pregnant WOCBP partners should use male contraception (i.e. condom) to avoid exposure of an existing embryo/fetus. Additional contraception requirements detailed in Inclusion Criterion No. 5 must be considered.

#### 4.3 TREATMENT COMPLIANCE

Compliance will be assured by administration of all trial medication in the study centre under supervision of the investigating physician or a designee. The measured plasma concentrations of trial medication will provide additional confirmation of compliance.

Subjects who are non-compliant (for instance, who do not appear for scheduled visits or violate trial restrictions) may be removed from the trial and the CRF will be completed accordingly (for further procedures, please see Section 3.3.4.1).

Proprietary confidential information © 2021 Boehringer Ingelheim International GmbH or one or more of its affiliated companies

## 5. ASSESSMENTS

#### 5.1 ASSESSMENT OF EFFICACY

Not applicable. No efficacy endpoints will be evaluated in this trial.

#### 5.2 ASSESSMENT OF SAFETY

#### 5.2.1 Physical examination

At screening, the medical examination will include demographics, height and body weight, smoking and alcohol history (results not mandatory to be entered into CRF or to be reported), relevant medical history and concomitant therapy, review of inclusion and exclusion criteria, review of vital signs (BP, PR, body temperature), 12-lead ECG, laboratory tests, and a physical examination. At the end of trial examination, it will include review of vital signs, 12-lead ECG, laboratory tests, and a physical examination including determination of weight.

